7.6 Medical Monitoring

It is the responsibility of the sponsor-investigator to oversee the safety of the study at his/her site. This safety monitoring will include careful assessment and appropriate reporting of adverse events as noted above, as well as the construction and implementation of a site data and safety-monitoring plan (see section 9 [“Study Monitoring, Auditing, and Inspecting”](#)). Medical monitoring will include a regular assessment of the number and type of serious adverse events.

7.6.1 Internal Data and Safety Monitoring Board

An independent Data and Safety Monitoring Board (DSMB) will be convened to assess the progress of a clinical study, the safety data, and critical immunogenicity endpoints. The members of the DSMB serve in an individual capacity and provide their expertise and recommendations. Members of the DSMB will not participate as investigators in the study under review and will not be supervised by study investigators.

Members of the DSMB will not have a direct interest in knowing or influencing trial outcome or have a financial or intellectual interest in the outcome of any studies under review.

The DSMB will include experts in transplantation, statistics, and infectious disease. The DSMB will have at least one biostatistician for each meeting review. A quorum will occur when two members are present. Without a quorum a meeting will not be held, unless alternate arrangements have been made by the Chair of the DSMB in agreement. The DSMB will review the study before initiation, at the midpoint of enrollment and at least yearly thereafter. *Ad hoc*

DSMB meetings can be initiated by a study Investigator and/or the Medical Monitor if a safety concern is identified at any time during the study. The DSMB will review study data to evaluate the safety, efficacy, study progress, and conduct of the study. If a concern is identified, the DSMB will recommend whether or not dosing should be discontinued or modified depending upon the event (type, severity, relationship to study treatment) and to recommend whether or not the study should continue.

8 Data Handling and Record Keeping

8.1 Confidentiality

Information about study subjects will be kept confidential and managed according to the requirements of the Health Insurance Portability and Accountability Act of 1996 (HIPAA). Those regulations require a signed subject authorization informing the subject of the following:

- What protected health information (PHI) will be collected from subjects in this study
- Who will have access to that information and why
- Who will use or disclose that information
- The rights of a research subject to revoke their authorization for use of their PHI

If a subject revokes authorization to collect or use PHI, the sponsor-investigator, by regulation, retains the ability to use all information collected prior to the revocation of subject authorization. For subjects that have revoked authorization to collect or use PHI, attempts should be made to obtain permission to collect at least vital status (long term survival status that the subject is alive) at the end of their scheduled study period.

8.2 Source Documents

Source data is all information, original records of clinical findings, observations, or other activities in a clinical trial necessary for the reconstruction and evaluation of the trial. Source data are contained in source documents. Examples of these original documents and data records include: hospital records, clinical and office charts, laboratory notes, memoranda, subjects' diaries or evaluation checklists, pharmacy dispensing records, recorded data from automated instruments, copies or transcriptions certified after verification as being accurate and complete, microfiches, photographic negatives, microfilm or magnetic media, x-rays, subject files, and records kept at the pharmacy, at the laboratories, and at medico-technical departments involved in the clinical trial.

8.3 Case Report Forms

The study case report form (CRF) is the primary data collection instrument for the study. All data requested on the CRF must be recorded. All missing data must be explained. If a space on the CRF is left blank because the procedure was not done or the question was not asked, write "N/D". If the item is not applicable to the individual case, write "N/A". All entries on paper

should be printed legibly in ink. If any entry error has been made, draw a single straight line through the incorrect entry and enter the correct data above it. All such changes must be initialed and dated. Do not erase or use “white-out” for errors. For clarification of illegible or uncertain entries, print the clarification above the item, initial and date it. If the reason for the correction is not clear or needs additional explanation, neatly include the details to justify the correction.

8.4 Data Management

Research material will be obtained from individually identifiable living human subjects through interactions with study members, review of medical records and blood specimens utilized for lab tests, obtained as part of the protocol. Individually identifiable patient history and medical record information will be stored under coded accession numbers. Clinical laboratory values are stored in the electronic medical record system of Mayo Clinic, requiring protected password access. These data are monitored regularly for access and a formal policy regarding protection of personal privacy is in place through Mayo Clinic. The key to identification of subjects will be maintained in a secure office environment under the direction of the sponsor-investigator.

8.5 Data Processing

A data coordinating group will monitor data collection and provide interim analyses to the Data Safety Monitoring Board. **We expect to complete Segment I enrollment within 6-9 months and have final data on the primary endpoint approximately 12 months from study start.** All patient outcome variables are tracked using registries set up in the “Healthy Planet” tool in the Electronic Health Record. For infection data, a registry flags patients as having an infection if a clinical diagnosis of COVID-19 was added to the problem list or a SARS-CoV-2 polymerase chain reaction test is positive. Those without laboratory confirmation are reviewed to ensure that this was appropriate (for example, an outside laboratory result not visible in our chart). External results could satisfy registry metrics if they could be identified within the interoperable framework for data sharing across the EHR, Care Everywhere (Epic Systems Corporation). A similar registry architecture captures data on vaccination data, populated from both EHR records, state health registries, and the health information exchange.

Data Security and Confidentiality

Source documents, CRFs and original consents will be stored in secured locations at Mayo Clinic. Clinical laboratory values are stored in the electronic medical record system requiring protected password access and approved use. Every individual who accesses a medical record has their activity tracked in the system. These data are monitored regularly for access and a formal policy regarding protection of personal privacy which is in place throughout Mayo Clinic.

Data Quality Assurance

Manual and computerized quality checks will occur during data collection and analyses and any discrepancies will require Case Report Form (CRF) review and validation of correct data.

Data Clarification Process

All queries will be logged and tracked electronically, as well as any corrections or justifications which are made, if applicable.

Records Retention

The sponsor-investigator will maintain records and essential documents related to the conduct of the study. These will include subject case histories and regulatory documents.

The sponsor-investigator will retain the specified records and reports for

1. Up to 2 years after the marketing application is approved for the drug; or, if a marketing application is not submitted or approved for the drug, until 2 years after shipment and delivery of the drug for investigational use is discontinued and the FDA has been so notified OR
2. As outlined in the Mayo Clinic Research Policy Manual –“Retention of and Access to Research Data Policy” [REDACTED] whichever is longer.

9 Study Monitoring, Auditing, and Inspecting

9.1 Study Monitoring Plan

The Investigator will allocate adequate time for such monitoring activities. The sponsor-investigator will also ensure the monitor or other compliance, or quality assurance reviewer has access to all study-related documents and study related facilities (e.g. pharmacy, diagnostic laboratory, etc.), and has adequate space to conduct the monitoring visit.

9.2 Auditing and Inspecting

The sponsor-investigator will permit study-related monitoring, audits, and inspections by the IRB, the funding sponsor, and government regulatory agencies, of all study related documents (e.g. source documents, regulatory documents, data collection instruments, study data etc.). The sponsor-investigator will ensure the capability for inspections of applicable study-related facilities (e.g. pharmacy, diagnostic laboratory, etc.).

Participation as an sponsor-investigator in this study implies acceptance of potential inspection by government regulatory authorities and applicable compliance offices.

10 Ethical Considerations

This study is to be conducted according to United States government regulations and Institutional research policies and procedures.

This protocol and any amendments will be submitted to a properly constituted local Institutional Review Board (IRB), in agreement with local legal prescriptions, for formal approval of the study. The decision of the IRB concerning the conduct of the study will be made in writing to the sponsor-investigator before commencement of this study.

All subjects for this study will be provided a consent form describing this study and providing sufficient information for subjects to make an informed decision about their participation in this study. This consent form will be submitted with the protocol for review and approval by the IRB for the study. The formal consent of a subject, using the approved IRB consent form, must be obtained before that subject undergoes any study procedure. The consent form must be signed by the subject or the subject's legally authorized representative, and the individual obtaining the informed consent.

11 Study Finances

11.1 Funding Source

This study is financed by Janssen Research and Development, LLC, who will also be providing study drug.

14.1 TTS AESI Form

The form below represents the type of information that may be collected in case of a suspected AESI in order to help adjudicate whether the event is a case of TTS. Additional data may be requested by the sponsor for investigation of the event.

Adverse Event of Special Interest Questionnaire (AESIQ) for Thrombosis with Thrombocytopenia Syndrome

Date of Report: [dd-MMM-yyyy]

1. Adverse Event Description

Participant's clinical signs and symptoms (circle)

Leg/Calf Edema	Pain in Leg/Calf	Hemoptysis
Dyspnea	Chest Pain/Discomfort	Syncope
Tachypnoea	Tachycardia	Cough
Loss of consciousness	Headache	Seizure
Visual impairment	Weakness	Impaired speech
Confusional state	Paresthesia	Gait disturbance

Other Symptoms:

Was patient on VTE prophylaxis? YES/NO

If yes, details:

14.2 Guillain-Barré Syndrome Symptoms

Guillain-Barré Syndrome is a disease that causes your body to attack your nerves. If you have the following symptoms, please seek immediate medical attention:

- Prickling, pins and needles sensations in your fingers, toes, ankles or wrists
- Weakness in your legs that spreads to your upper body
- Unsteady walking or inability to walk or climb stairs
- Difficulty with facial movements, including speaking, chewing or swallowing
- Double vision or inability to move eyes
- Severe pain that may feel achy, shooting or cramplike and may be worse at night
- Difficulty with bladder control or bowel function
- Rapid heart rate (this is already included)
- Low or high blood pressure (this is already included)
- Difficulty breathing

14.3 Symptoms of Infection with Coronavirus-19 (SIC)

The following questions ask about symptoms people with coronavirus-19 infection may experience. Answer each question carefully by choosing ‘yes’ if you have experienced the symptom or ‘no’ if you have not experienced the symptom in the last 24 hours. If you choose ‘yes’, select the rating that best matches your experience.

In the last 24 hours, have you experienced...	Please rate the severity of each symptom you experienced.											
Feeling generally unwell (run down) Yes No If yes, →	How severe was your feeling (generally unwell or run down) in the last 24 hours?											
												
	0	1	2	3	4	5	6	7	8	9	10	
	None											Worst possible
Fatigue (tiredness) Yes No If yes, →	How severe was your fatigue (tiredness) in the last 24 hours?											
												
	0	1	2	3	4	5	6	7	8	9	10	
	None											Worst Possible
Physical weakness Yes No If yes, →	How severe was your feeling of physical weakness in the last 24 hours?											
												
	0	1	2	3	4	5	6	7	8	9	10	
	None											Worst Possible
Cough Yes No If yes, →	How severe was your cough in the last 24 hours?											
												
	0	1	2	3	4	5	6	7	8	9	10	
	None											Worst Possible
Shortness of breath (difficulty breathing) Yes No If yes, →	How severe was your shortness of breath (difficulty breathing) in the last 24 hours?											
												
	0	1	2	3	4	5	6	7	8	9	10	
	None											Worst Possible
Sore throat Yes No If yes, →	How severe was your sore throat in the last 24 hours?											
												
	0	1	2	3	4	5	6	7	8	9	10	
	None											Worst possible
Nasal congestion (stuffy nose) Yes No If yes, →	How severe was your nasal congestion (stuffy nose) in the last 24 hours?											
												
	0	1	2	3	4	5	6	7	8	9	10	
	None											Worst possible

Wheezing (whistling sound while breathing) Yes No If yes, →	How severe was your wheezing (whistling sound while breathing) in the last 24 hours?  0  1  2  3  4  5  6  7  8  9  10 None Worst possible
Runny nose Yes No If yes, →	How severe was your runny nose in the last 24 hours?  0  1  2  3  4  5  6  7  8  9  10 None Worst possible
Sneezing Yes No If yes, →	How severe was your sneezing in the last 24 hours?  0  1  2  3  4  5  6  7  8  9  10 None Worst possible
Chest congestion (mucus in chest) Yes No If yes, →	How severe was your chest congestion (mucus in chest) in the last 24 hours?  0  1  2  3  4  5  6  7  8  9  10 None Worst possible
Chest pain/ pressure/tightness Yes No If yes, →	How severe was your chest pain/pressure/tightness in the last 24 hours?  0  1  2  3  4  5  6  7  8  9  10 None Worst possible
Muscle aches/pains Yes No If yes, →	How severe were your muscle aches or pains in the last 24 hours?  0  1  2  3  4  5  6  7  8  9  10 None Worst possible
Joint aches/pains Yes No If yes, →	How severe were the aches or pains in your joints in the last 24 hours?  0  1  2  3  4  5  6  7  8  9  10 None Worst possible
Headache Yes No If yes, →	How severe was your headache in the last 24 hours?  0  1  2  3  4  5  6  7  8  9  10 None Worst possible
Feeling faint Yes No If yes, →	How severe was your feeling of faintness in the last 24 hours?  0  1  2  3  4  5  6  7  8  9  10 None Worst possible

Problems thinking clearly/brain fog Yes No If yes, →	How severe were your problems thinking clearly/brain fog in the last 24 hours?  0  1  2  3  4  5  6  7  8  9  10 None Worst possible
Chills Yes No If yes, →	How severe were your chills in the last 24 hours?  0  1  2  3  4  5  6  7  8  9  10 None Worst possible
Skin rash Yes No If yes, →	How severe was your skin rash in the last 24 hours?  0  1  2  3  4  5  6  7  8  9  10 None Worst possible
Eye irritation/discharge Yes No If yes, →	How severe was your eye irritation/discharge in the last 24 hours?  0  1  2  3  4  5  6  7  8  9  10 None Worst possible
Diarrhea Yes No If yes, →	How severe was your diarrhea in the last 24 hours?  0  1  2  3  4  5  6  7  8  9  10 None Worst possible
Vomiting Yes No If yes, →	How severe was your vomiting in the last 24 hours?  0  1  2  3  4  5  6  7  8  9  10 None Worst possible
Nausea Yes No If yes, →	How severe was your nausea in the last 24 hours?  0  1  2  3  4  5  6  7  8  9  10 None Worst possible
Abdominal/stomach pain Yes No If yes, →	How severe was your abdominal/stomach pain in the last 24 hours?  0  1  2  3  4  5  6  7  8  9  10 None Worst possible
Loss of appetite Yes No If yes, →	How severe was your loss of appetite in the last 24 hours?  0  1  2  3  4  5  6  7  8  9  10 None Worst possible

What was your **highest temperature** in the last 24 hours? ____ °C/°F

What method did you use to take your temperature?

oral **armpit** **ear** **forehead** **rectal**

In the last 24 hours, have you experienced...

Uncontrollable body shaking/shivering*

Yes **No**

Decreased sense of smell*

Yes **No**

Decreased sense of taste*

Yes **No**

Red or bruised looking feet or toes*

Yes **No**

*Please rate the severity of your symptoms in the last 24 hours?

No Symptoms

Mild

Moderate

Severe

14.4 Risk Factor Assessment

Are you a student?  Yes  No	If Yes – Are you likely to return to school in person in the near future?  Yes  No  I don't know														
Are you retired?  Yes  No	How often do you go in person to your main workplace (other than work-from-home)?  0 days/week  1 day/week  2-4 days/week  5 or more days/week														
Does your main workplace have social distancing measures in place?  Yes  No  I don't know  Not applicable															
Is your main workplace cleaned on a regular basis?  Yes  No  I don't know  Not applicable															
Do people in your main workplace use personal protection equipment (such as masks)?  Yes  No  I don't know  Not applicable															
How do you get to work? (Check all that apply)  Drive own car  Carpool  Rideshare (Taxi, Uber, Lyft, others)  Bus  Train / Subway  Walk / Bike  Frequent Air Travel  Not applicable															
On a typical day, how many people do you interact with in person at work?  No one  Between 1 and 10 people  Between 11 and 30 people  Between 31 and 50 people  More than 50 people															
On a typical day, how many people do you interact with in person outside of work?  No one  Between 1 and 10 people  Between 11 and 30 people  Between 31 and 50 people  More than 50 people															
Living Situation Do you live in any of the following (choose all that apply): 
  
  Single family home	 Multi-family housing (apartment building, condo)	
 
  Long-term care facility	 Assisted-living facility	
 
  Dormitory	 RV / Trailer	
 
  Single room in a hotel	 Shelter	
 
  Other adult group setting	 Staying with friends / Couch surfing	
 
  No residence	 Tribal Lands / Reservation	
 
  Other		
  
		 Single family home	 Multi-family housing (apartment building, condo)	 Long-term care facility	 Assisted-living facility	 Dormitory	 RV / Trailer	 Single room in a hotel	 Shelter	 Other adult group setting	 Staying with friends / Couch surfing	 No residence	 Tribal Lands / Reservation	 Other	
 Single family home	 Multi-family housing (apartment building, condo)														
 Long-term care facility	 Assisted-living facility														
 Dormitory	 RV / Trailer														
 Single room in a hotel	 Shelter														
 Other adult group setting	 Staying with friends / Couch surfing														
 No residence	 Tribal Lands / Reservation														
 Other															
How many people do you live with (other than yourself)? Total people under 18 years of age Total people between 18-64 years of age Total people over 65 years of age															
Are any of the people you live with expected to return to school in person in the near future?  Yes  No  I don't know															
Community Interactions In the last 2 weeks, have you attended any gatherings with more than 10 people? (e.g., church, party, concert, wedding, funeral, demonstration or other event).  Yes  No  Not applicable / Don't want to tell If yes, approximately how many people were at the largest gathering?  less than 10  10-20  21-50  51-250  More than 250															
Was this gathering an indoor or outdoor event?  Indoor  Outdoor  Both															
How frequently do you have visitors in your residence including people completing work inside?  Daily  Weekly  Monthly  Rarely  Never  N/A															
Over the past month, have you been in close contact with anyone that tested positive for COVID-19?  Yes  No  I don't know  Not applicable / Don't want to tell If yes, is this person someone that you live with?  Yes  No  Not applicable / Don't want to tell															

14.5 Kidney Transplant Follow Up Questionnaire**Kidney Transplant Follow-Up Questionnaire****General Questions****Answer**

Since your last visit, have you recently visited the hospital emergency room, urgent care facility or an afterhours clinic? Yes No
 _____ visits (enter '00' if no visits)

Since your last visit, have you recently been admitted hospitalized? Yes No
 (Stayed in the hospital overnight)

	Admission Date (MM,DD,YYYY)	Reason for admission	Discharge Date (MM,DD,YYYY)
Hospitalization #1	__ / __ / ____ MM/DD/YYYY		__ / __ / ____ MM/DD/YYYY
Hospitalization #2	__ / __ / ____ MM/DD/YYYY		__ / __ / ____ MM/DD/YYYY

Have you recently been diagnosed with a new infection? Yes No
 Example Urinary Tract Infection (UTI), Cytomegaly Virus (CMV), etc.
 If Yes, When? _____ Was it treated? _____

Have you recently been diagnosed with any malignant cancer? Yes No
 If Yes, When? _____ Was it treated? _____

Have you recently experienced a heart attack, Transient Ischemic Attack (TIA) or stroke? Yes No
 If Yes, When? _____ Was it treated? _____

Have you had any unintended weight loss or gain in the last year? Yes No
 If Yes, When? _____ Was it treated? _____

Have you been treated for rejection or have any acute rejection episodes? Yes No
 If Yes, When? _____ Was it treated? _____

Have you been diagnosed with any major illness? Yes No
 If Yes, When? _____ Was it treated? _____

Immunosuppression Medications

Name of medication	Dose	Frequency	Time	Comments

Immunosuppression Medication Adherence

Which number best describes your medication adherence? ____

1.	Never missed a dose
2.	Missed 1-2 times a week
3.	Missed 1-2 times a month
4.	Pro-long periods. I'm unable to get my immunosuppression medications

14.6 COVID-19 Surveillance and Evaluation Questionnaire

1. Have you had close contact with a person with a LABORATORY CONFIRMED case of COVID-19? Close contact is defined by CDC as:
 1. Being within approximately 6 feet of a COVID-19 patient for a prolonged period of time (more than 5 minutes)
 2. Having direct contact with infectious secretions of a COVID-19 case (e.g. being coughed on)

Yes/No

In the last 48 hours, have you had ANY of the following?

3. a fever of 100.5 F (38 C) or greater, OR
4. new cough, OR
5. new shortness of breath, OR
6. new sore throat, OR
7. new diarrhea, OR
8. new fast breathing (respiratory distress), OR
9. new chills, OR
10. new muscle aches (myalgias), OR
11. new loss of smell, OR
12. new change or loss of taste sensation

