3.3 Duration of Participation

Subjects who only participate in Segment I will be followed for 2 years after receiving the Janssen Ad26.CoV2.S vaccine. Those who participate in Segment II will have their participation extended, with 2 years of clinical follow up after receiving the second Janssen Ad26.CoV2.S vaccine date. Screened patients not receiving the Janssen Ad26.CoV2.S vaccine will be followed for 2 years.

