3.5 Secondary Study Assessments/Endpoints

- Any response in non-responders: Number and percentage of patients with undetectable anti-SARS-CoV-2 spike protein antibody level after 2 or more doses of mRNA vaccine who receive the Janssen Ad26.CoV2.S vaccine who develop anti-SARS-CoV-2 spike protein antibody levels >0 or <250 at 28 days.
- Good response in low-responders: Number and percentage of patients with anti-SARS-CoV-2 spike protein antibody levels >0 but <250 U/ml after 2 or more doses of mRNA vaccine who receive the Janssen Ad26.CoV2.S vaccine who develop anti-SARS-CoV-2 spike protein antibody levels ≥ 250 at 28 days.
- Segment II. Rate of achieving an anti-SARS-CoV-2 spike protein antibody level ≥ 250 U/ml 28 days after receiving the Janssen Ad26.CoV2.S vaccine in patients who failed to achieve the response in Segment I who received a second dose of the Janssen Ad26.CoV2.S vaccine after adjustment of immunosuppression.
- Durability of anti-SARS-CoV-2 spike protein antibody levels in patients who developed any level of antibody response after receiving the Janssen Ad26.CoV2.S vaccine at 180 days and/or between 1 and 2 years after receiving the Janssen Ad26.CoV2.S vaccine.
- Incidence of COVID-19 infection at 2 years.

Exploratory Endpoints (Mechanistic studies):

Baseline Differences

It is expected that at baseline (prior to receiving the Janssen Ad26.CoV2.S vaccine), when compared to responders, low responders and non-responders will demonstrate no SARS-CoV-2 specific T and B cells and lower mean number of T cell receptors. Non-responsiveness will correlate with lower mean numbers of T and B cells including specific subtypes such as T-helper cells and memory B cells.

Response to Alterations in Immunosuppression

Alterations in immunosuppression will lead to increased number of T and B cells from baseline. Paired t test with each patient serving as their own controls.

Additional Dose with the Janssen Ad26.CoV2.S Vaccine

Compared to those who do not respond, patients who respond to receiving the Janssen Ad26.CoV2.S vaccine will demonstrate new or increased levels of SARS-CoV-2-specific T and B cells. They also will have higher baseline levels of T cells, B cells, serum immunoglobulin levels and T cell repertoire.

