6.1 Segment I

6.1.1 Day - 21 (-30 /+7 Days)

Potential subjects will be identified by review of their medical record. If a participant is identified by review of the report, they will be contacted via the Mayo Clinic portal, the online patient communication system, phone or e-mail (if the potential subject has already contacted the study team in this manner). Study details, procedures, risks, and benefits will be described to patients interested in participation. Subjects will be consented for study participation either via telephone or at Mayo Clinic, depending on patient preference. The participant's medical history, demographics, concomitant medications and therapies, immunosuppression medications and clinical outcomes (current health and graft status) will be collected. Subjects will complete the COVID-19 Surveillance and Evaluation questionnaire (Section 14.6). Relevant medical procedures which are performed as part of the participants clinical care up to 60 days prior to signing of consent, such as clinical laboratory results may be used for determining study eligibility.

Blood for anti-SARS-CoV-2 spike protein antibody and anti-SARS-CoV-2 nucleocapsid total antibody testing will be drawn locally and sent overnight to Mayo Clinic-Rochester Laboratory for

testing. Not all screening procedures need to occur in one day. After consent is obtained, screening procedures can be completed on any day up to the baseline visit.

Patients who meet criteria will be contacted and scheduled to receive the Janssen Ad26.CoV2.S vaccine. They will be required to travel to one of the 3 Mayo Clinic transplant centers to receive the vaccine. There will be 3 groups:

1. Low-responders (n=100)
2. Non-responders (n=300)—Randomized after obtaining evidence that anti-SARS-CoV-2 spike protein antibody levels = 0 U/mL. Patients are stratified by the number of mRNA vaccines they received (2 or more).
 - a. Dosing with the Janssen Ad26.COVID-19 vaccine without immunosuppression adjustment
 - b. Dosing with the Janssen Ad26.COVID-19 vaccine with immunosuppression adjustment.

Subjects randomized to receive immunosuppression adjustment will follow one of the regimens outlined in Section 5.2.1. If randomized to the immunosuppression group, they will be contacted via phone by a physician with instruction on the participant's new immunosuppression regimen.

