6.1.5 Days 14 (+/- 7 Day) and 28 (+/- 7 Days)

Anti-SARS-CoV-2 spike protein antibody and anti-SARS-CoV2 nucleocapsid total antibody levels will be obtained during these study event periods. Study team will record any changes to concomitant and immunosuppressant medications or therapies, as well as changes to health status to determine any potential adverse events. Blood will be collected for a platelet count and for mechanistic studies (Day 28 only). After Day 28, subjects randomized to a change in their immunosuppression medication will revert back to their original regimen. COVID-19 symptoms will be assessed to determine if the subject has experienced any COVID-19 symptoms or recently been tested. Patient and graft status information will also be collected. The study team will review and complete the safety follow up questionnaires with the subject.

If necessary, a symptom directed physical exam can be performed.

Segment II (described in Section 6.2) will begin on Day 28 for individuals whose immunosuppression regimen was not changed and continue to have low to no response levels for their COVID-19 spike protein test.

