Visit Description	Screening visit		Janssen Ad26.COV2.S vaccine	Follow up						Safety		
Visit Window	-30 / +7 Days	+/- 3 days	-4/+1 day	+/- 1 Day	+/- 2 Day	+/- 7 Day	+/- 7 Days	+/- 15 Days	+/- 30 Days	+/- 60 Days	+/- 60 Days	N/A

Safety assessment AFTER vaccination

Subject Symptom Report ^b			Continuous									
Diary compliance phone call				X								
Safety follow-up phone call ^c					X							
Symptom Directed Exam as needed						X	X	X	X			X
Safety Follow Up Questionnaires ^d			X	X	X	X			X	X	X	
COVID-19 Surveillance and Evaluation ^e	X	X ^f	X			X	X	X	X	X	X	X
Patient and Graft Status	X	X	X			X	X	X	X	X	X	X
MAAE Monitoring ^g				Continuous								
(S)AE Monitoring ^h				Continuous								

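### The COVID-19 surveillance form has a 48-hour symptom window and no question on a positive test since the last contact, so infections diagnosed elsewhere can be missed, mainly after Day 180 and unequally between groups

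*Combined protocol and SAP*

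**What the plan says.** Section 3.5 lists as a secondary endpoint "Incidence of COVID-19 infection at 2 years". Section 6.8 tests it in the 400 vaccinated patients by a one-sample log-rank test against 10% per year.

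Form 14.6 has two parts. The first asks "Have you had close contact with a person with a LABORATORY CONFIRMED case of COVID-19" and sets no time limit. The second lists symptoms under "In the last 48 hours, have you had ANY of the following". Neither part asks about a positive test or a diagnosis. Section 6.1.1 names this form at screening. In the schedules of Section 6.6 the row "COVID-19 Surveillance and Evaluation" recurs through follow-up, and for the vaccinated groups it is footnoted to Section 6.5.

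Infections can also be recorded in other ways:
- Section 8.5: an EHR registry flags a problem-list diagnosis or a positive PCR at any time. For outside results, "External results could satisfy registry metrics if they could be identified within the interoperable framework for data sharing".
- Sections 6.5.1 and 6.5.2: a positive RT-PCR from an outside laboratory meets the criteria for suspected COVID-19 and is entered as an unscheduled visit.
- Section 6.1.5, Days 14 and 28: "COVID-19 symptoms will be assessed to determine if the subject has experienced any COVID-19 symptoms or recently been tested". Section 6.1.3 has a similar question at baseline.
- Sections 3.1.5, 6.1.6 and 6.1.7: nucleocapsid antibody is measured through Day 180, at Year 1 only if Day 180 levels are detectable, and not at Year 2.
- Section 6.1.7: Years 1 and 2 rest on medical record review, with some questionnaires at Year 1.
- Sections 7.2 and 7.3: adverse events are sought by questioning at each contact. Medically attended events are reported to 6 months after the last dose and serious events throughout.

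**The concern.** A 2-year incidence endpoint needs each contact to look back over the whole interval since the previous one. After Day 28 the Segment I contacts are about two, three, six and then twelve months apart, yet the symptom part of the form looks back two days. A patient who tested positive elsewhere and recovered between contacts can answer every item truthfully without the infection coming to light. If the outside result does not reach the EHR and the patient does not volunteer it, the infection may not be counted.

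Two analyses are exposed. In the one-sample test against 10% per year, infections missed beyond those missed in the historical rate lower the observed rate and look like a reduction. In comparisons with initial responders, whom Sections 3.1.3 and 6.3 name as a comparison group, a difference in how hard each group is looked at can be read as a difference in infection.

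**Working it through.** **Time covered by the form's symptom window.** Segment I follow-up is two years ("Subjects who only participate in Segment I will be followed for 2 years after receiving the Janssen Ad26.CoV2.S vaccine"), or 730 days. Each use of the form covers 2 days.
- Schedule 2C, six post-dose times (Days 14, 28, 90, 180, Years 1, 2): 6 × 2 / 730 = 1.6%. With Day 0: 14/730 = 1.9%.
- Schedule 2A, which as extracted shows no Year 2 mark: 10/730 = 1.4%.
- Initial responders (Years 1 and 2): 4/730 = 0.5%.
- Segment II counted from the first dose, eleven times including Day 0: 22 / (730 + 56) = 2.8%.

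These are shares of days for one form, not shares of infections. If symptoms last D days, six uses could touch 6 × (2 + D)/730 of symptomatic infections. For an assumed D of 5 to 14 days that is 42/730 to 96/730, about 6% to 13%, from the form alone.

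**The plan's own figure for this endpoint.** Section 6.8 states 90% power for 7% against 10% per year with 400 patients. Take hazards h = −ln(1 − annual rate), T = 2 years, no losses, and Z = (O − E)/√E. Person-years are n(1 − e^(−hT))/h. With h0 = −ln 0.90 and h1 = −ln 0.93, E = 78.5 and O = 54.0. Power = Φ{[(E − O)/√E − z]/√(O/E)}.
- One-sided 0.05 (z = 1.645): (2.757 − 1.645)/0.830 = 1.34, power 91%.
- Two-sided 0.05 (z = 1.960), the default in Section 6.7: (2.757 − 1.960)/0.830 = 0.96, power 83%.

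So the formula reproduces the stated power, but only as a one-sided test. That is a separate matter. The false-reduction figures below use the two-sided default, with 2.5% in the lower tail.

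**Effect of missed infections.** Let the true rate be 10% per year, so the null is true. Let m be the share of infections missed beyond the share missed in the historical rate. The observed hazard is taken as (1 − m) × h0, and the chance of a false reduction follows from the same expression with z = 1.960.

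| m (assumed) | Observed annual rate | E | O | Chance of a false reduction |
|---|---|---|---|---|
| 0 | 10.0% | 76.0 | 76.0 | 2.5% |
| 5% | 9.5% | 76.4 | 72.6 | 5.9% |
| 10% | 9.05% | 76.8 | 69.1 | 12.7% |
| 20% | 8.1% | 77.6 | 62.1 | 41% |
| 30% | 7.1% | 78.4 | 54.9 | 80% |

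Example, m = 10%: (76.8 − 69.1)/√76.8 = 0.88; (0.88 − 1.96)/√0.90 = −1.14; Φ(−1.14) = 0.127. An excess of about 31% (1 − ln 0.93/ln 0.90) would turn a true 10% into an observed 7%, the plan's own alternative.

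**Intensity of capture by group.** Segment I patients have up to six post-dose surveillance times, serology through Day 180, and adverse event reporting. Schedule of Events 1 gives initial responders surveillance at Years 1 and 2 only, no nucleocapsid test after screening, and no adverse event row. Registry and record review apply to both.

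**The case against.** The strongest reply is that the endpoint does not rest on this form. Section 8.5 says outcome variables are tracked through registries, which are not tied to visit windows. Record review at Years 1 and 2 looks back over the interval. Nucleocapsid antibody can show an infection nobody reported, and Section 5.6 has COVID-19 therapies captured throughout. Form 14.5 asks about new infections, major illness, and emergency or hospital visits. The historical 10% comes from the same patient population. If it was captured equally well or badly, the one-sample test has no bias from this source.

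Most of this stands. A reader might infer from the 48-hour window that under 2% of the endpoint is observed. The documents do not support that: the percentage describes days inside one form's symptom window. A reader might also infer that missed infections must look like protection. That holds only for the one-sample test, and only if study capture falls below the capture behind the 10%. Against initial responders the bias can run either way.

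The reply does not close the later gap:
- Section 6.1.6 describes its visits as the last direct contact in Segment I, although Section 6.1.7 adds questionnaires at Year 1.
- The registry counts an outside result only if it can be found. A positive test other than PCR enters only through the problem list.
- The outside RT-PCR route depends on the patient volunteering the result. The recent-testing question is described only at baseline and Days 14 and 28.
- Late serology is conditional at Year 1 and absent at Year 2. Sections 6.8 and 8.5 do not say that seroconversion counts as an endpoint infection.
- Form 14.5 is scheduled in Segment I at baseline and Year 1, asks about infections diagnosed recently, and is not scheduled for initial responders.

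**Conclusion.** The point holds as a modest gap in ascertainment. Form 14.6 has no positive-test or diagnosis item, and its symptom window spans under 2% of follow-up days in Segment I and about 0.5% in initial responders. Several other routes find infections, so the exposure is limited to those diagnosed elsewhere and not visible in the EHR, mainly after Day 180, and to unequal intensity between groups.

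The one-sample test is sensitive to this: an excess miss of 5% to 30% raises the chance of a false reduction from 2.5% to between about 6% and 80%. The excess itself is an assumption. The documents give neither the share the study would miss nor how the historical 10% was ascertained, and the calculation assumes constant hazards and no losses. Confidence is moderate. The endpoint is secondary, and the change is worth making chiefly because it is cheap.

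**What to change.** Add one item to Form 14.6: *Since your last study contact, have you had a positive COVID-19 test or been told you had COVID-19? If so: date, type of test, where, and whether hospitalized.* Put it to all groups, initial responders included, at every scheduled surveillance time including Years 1 and 2. State in Section 6.8 that an infection counts if it comes from this item, after checking, or from the registry, and record the source so that capture can be compared between groups.

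The cost is one CRF field, a brief patient query at Year 2 where Section 6.1.7 now describes only record review, and some self-reports to verify. The item cannot repair an unknown shortfall in the historical rate. A sentence on how the 10% was ascertained would let readers judge the one-sample comparison.
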